### 6.4.4. Subgroup Analysis

The following selected subgroups may be performed for subgroup analysis for the primary efficacy endpoint, i.e. the proportion of patients with clinical cure rate at Day 21 as assessed by the investigator based on the micro-ITT Population.

- Randomization stratum: Geographic regions (Americas, Eastern EU, Western EU, versus Asia)
- Randomization stratum:  $\text{PaO}_2/\text{FiO}_2 >200$  versus  $\leq 200$
- APACHE score  $\geq 20$  versus  $< 20$  at baseline
- Monopathogen (*P. aeruginosa* only) versus multiple pathogens in baseline culture
- Multi Drug Resistant (MDR) versus susceptible for *P. aeruginosa* at baseline
- Reason for admission to ICU at baseline (Trauma versus Non-trauma)
- Rapid test only versus culture confirmed randomization
- Age ( $< 65$  years versus  $\geq 65$  years)

In addition, the above subgroup analysis will also be performed for the selective secondary efficacy endpoints, i.e. the proportion of patients with clinical cure rate at Day 7, Day 14, and Day 28 as assessed by the investigator based on the micro-ITT Population.

### **6.5. Pharmacokinetic Analyses**

Pharmacokinetic endpoints include the assessment of the PK parameters during full PK sub-study and during sparse PK sub-study.

For full PK sub-study, for each patient participating in the FULL PK sub-study, a total of ten (10) PK samples will be obtained. Sampling times are as follows:

- Prior to the beginning of infusion (pre-dose, time 0)
- 2 hours (end of infusion),
- 4 hours,
- 12 hours,
- 24 hours,
- 96 hours (Day 4 visit),
- 168 hours (Day 7 visit),
- 336 hours (Day 14 visit),
- 504 hours (Day 21 visit),
- 672 hours (Day 28 visit).

A non-compartmental analysis will be performed to characterize the PK of Aerucin® for the full PK sub-study.

For sparse PK sub-study, for subjects participating in the SPARSE PK sub-study, four (4) PK samples will be obtained for each at the following times:

- Prior to the beginning of infusion (pre-dose, time 0)
- 2 hours (end of infusion),
- at any one of the following timepoints: 4h 12h, or 24h post-dose initiation (inclusive),
- at any of the following visits: Day 4, 7, 14, 21, or 28.

A population PK (compartmental modeling) approach will be used to characterize the PK of Aerucin® for the sparse PK population.

All pharmacokinetic analyses will be performed by another vendor and described in a standalone PK analysis plan.

### **6.6. Safety Analyses**

Safety data will be summarized by actual treatment received and in total based on the Safety Population.

### **6.6.1. Adverse Events**

An AE is defined as any untoward medical occurrence in a clinical investigation subject administered a pharmaceutical product, which does not necessarily have a causal relationship with this treatment. Adverse events, which include clinical laboratory test variables, will be monitored and documented from the time of randomization until 28 days after last dose. Adverse events will be coded using MedDRA (Version 19.1). Treatment-emergent adverse events (TEAEs) are defined as AEs that start on or after the administration of the study drug.

An overview of AEs will be provided including counts and percentages of subjects with the following:

- Any AEs
- Any TEAEs (overall and by maximum severity)
- Any drug-related TEAEs (overall and by maximum severity)
- Any serious AEs (SAEs) (overall and by maximum severity)
- Any drug-related serious AEs (overall and by maximum severity)
- Any treatment-emergent serious AEs (TESAEs)
- Any TEAEs leading to discontinuation of study drug
- Any AEs leading to death

The number and percentage of subjects with at least one TEAE will be presented by system organ class and preferred term. Drug-related TEAE, SAEs, Drug-related SAEs, and TESAEs will be summarized in the same manner. In the case of multiple occurrences of the same AE within the same subject, each subject will be counted only once for each SOC and preferred term.

Summaries will be provided by maximum severity for the number and percentage of subjects with TEAEs by system organ class and preferred term. For this summary, subjects with multiple adverse events will be counted only once by the maximum severity with in an SOC and preferred term.

Subject listings of SAEs, TEAEs leading to discontinuation of study drug, and AEs leading to death will be provided. All adverse events will be listed.

### **6.6.2. Clinical Safety Laboratory Evaluations**

#### **Standard safety laboratory tests**

Standard safety laboratory tests are required at screening/baseline, Day 4, 7, 14, 21 and 28, except pregnancy testing (screening/baseline only). All the following tests will be performed by the local laboratory.

- Chemistry:
  - Miscellaneous: glucose, osmolality, bicarbonate, total protein, albumin
  - Electrolytes: sodium, potassium, chloride, calcium

- Liver function: total bilirubin, alanine transaminase (ALT), aspartate transaminase (AST), lactate dehydrogenase (LDH), alkaline phosphatase
- Miscellaneous enzymes: creatine kinase (CK), amylase, C-reactive protein (CRP)
- Renal function: blood urea nitrogen (BUN), creatinine, serum glomerular filtration rate (eGFR), phosphorus
- Hematology & coagulation
  - Red blood cell (RBC), hemoglobin, hematocrit
  - WBC, neutrophils, lymphocytes, basophils, eosinophils, and monocytes (absolute counts or %)
  - INR, fibrinogen, platelets
- Urine: glucose, protein, RBC, WBC
- Pregnancy test for women of childbearing potential (serum or urine, screening only)

Laboratory test results (Chemistry, Hematology, and Coagulation) at each scheduled visit and change from baseline will be summarized by treatment group and in total.

Shift tables, showing individual subject changes from baseline to each post baseline time point will be presented for each laboratory parameter, by treatment group, using the normal, abnormal categorization noted below.

- Normal: result is within the local lab normal range
- Abnormal: result is either higher or lower than the normal range

All clinical laboratory data will be listed. Values outside the normal ranges will be flagged.

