4.1 Inclusion Criteria

1. Written Informed Consent given by the patient or, if not possible, by a legally authorized representative and/or an independent physician as authorized by the competent ethics committee (EC) or independent review board (IRB) and local regulations.

2. To be at least 18 years of age.

For Taiwan: To be at least 20 years of age.

South Korea only: To be at least 19 years of age.

3. To be treated in an ICU at the time of enrollment.

4. Endotracheal tube in place (tracheostomy is allowed).

5. The patient is mechanically ventilated.

6. Diagnosis of pneumonia based on the following criteria (a, b, c, all must be met):

a. One definitive chest X-ray diagnostic of pneumonia,

or

A sequence of at least 2 chest X-rays showing the presence of new or progressive infiltrate(s) suggestive of bacterial pneumonia.

b. Hypoxemia based on at least one of the following measurements/criteria:

i. $\text{PaO}_2/\text{FiO}_2 < 250$ mmHg (at sea level or equivalent for significant elevations above sea level) while intubated and mechanically ventilated, as one or more measures within ≤ 24 hours prior to randomization, or

ii. $\text{PaO}_2 < 60$ mmHg (at sea level or equivalent for significant elevations above sea level) while intubated and mechanically ventilated, as one or more measures within ≤ 24 hours prior to randomization), or

iii. Respiratory failure necessitating intubation and mechanical ventilation. If tracheostomy is in place, the need for mechanical ventilation.

c. At least one of the following signs:

i. Documented fever (e.g., body temperature greater than or equal to 38° Celsius).

ii. Hypothermia (e.g., core body temperature less than or equal to 35° Celsius).

iii. Total peripheral white blood cell (WBC) count greater than or equal to 10,000 cells/ μL (or mm^3).

iv. Leukopenia with total WBC less than or equal to 4,500 cells/ μL (mm^3).

v. Greater than 15 percent immature neutrophils (bands) noted on peripheral blood smear.

7. Documented pulmonary infection with *P. aeruginosa* obtained by BAL, mini-BAL, protected ETA (collectively ‘airway specimen’). For the study randomization, *P. aeruginosa* must be identified by one of the three methods below:

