Clinically significant abnormal laboratory or other examination (e.g. electrocardiogram) findings independent from the underlying medical condition that are detected during the study or are present at prior to Day 0 and significantly worsen during the study should be reported as adverse events. The Investigator will exercise his or her medical and scientific judgment in deciding whether an abnormal laboratory finding, or other abnormal assessment is clinically significant. Clinically significant abnormal laboratory values occurring during the clinical study will be followed until repeat tests return to normal, stabilize, or are no longer clinically significant. Any abnormal test that is determined to be an error does not require reporting as an adverse event.

Worsening of the index infection due to insufficient therapeutic effect of study drug is captured as an efficacy measure (i.e., clinical failure) and in general will not be considered an AE. However, if the worsening of the index infection meets seriousness criteria (see Section 8.3), the event will be deemed an SAE.

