9.3.2 Safety analysis

Safety evaluations will include treatment emergent adverse events, vital signs, physical exam, and laboratory values. Safety will be summarized by treatment group. All treatment emergent adverse events, and serious adverse events, will be coded using the Medical Dictionary for Regulatory Activities (MedDRA). Relationship to treatment, as well as severity will also be summarized. Changes in vital signs and physical exam will be summarized by group. Changes in laboratory values, as well as shifts (normal-> abnormal) will be summarized by treatment group.

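### The laboratory shift tables pool high and low values as abnormal, so they cannot show the direction of a change

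*SAP*

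**What the plan says.** SAP 6.6.2 (Standard safety laboratory tests) plans a shift table for each laboratory parameter, by treatment group, from baseline to each later time point, "using the normal, abnormal categorization noted below". The two categories are "Normal: result is within the local lab normal range" and "Abnormal: result is either higher or lower than the normal range". Protocol 9.3.2 is consistent with this: "Changes in laboratory values, as well as shifts (normal-> abnormal) will be summarized by treatment group".

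The same SAP section plans two other outputs. One is a summary by visit: "Laboratory test results (Chemistry, Hematology, and Coagulation) at each scheduled visit and change from baseline will be summarized by treatment group and in total". The other is a set of listings: "All clinical laboratory data will be listed. Values outside the normal ranges will be flagged". SAP 6.1.2 gives the statistics for continuous data as n, mean, median, standard deviation, minimum and maximum.

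Neither document plans a low/normal/high shift, a graded shift, a table of markedly abnormal values or a shift to the worst post-baseline value.

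**The concern.** A shift table is useful because it follows individual subjects against a reference range, by arm. With high and low merged, it can say that a subject left the range but not on which side. It cannot register a subject who crossed from one side to the other.

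For white cells, platelets, potassium and glucose, the two sides have different clinical meanings. An arm in which platelets fall below range and an arm in which they rise above it could produce the same table.

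Laboratory safety is one of three named safety endpoints (Protocol 8.1, SAP 5.5). The human experience the protocol cites is 16 healthy volunteers (Protocol 1.5.1 and 5.2). This placebo comparison is therefore where a laboratory effect in patients would be looked for.

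**Working it through.** The plan states no figure on this point, so there is none to reproduce. The check is to map every low (L), normal (N), high (H) transition onto the SAP's two categories, with L and H both becoming A (abnormal).

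| Baseline → post-baseline | SAP cell | Seen as a shift? | Direction visible? |
|---|---|---|---|
| N → L | N → A | yes | no |
| N → H | N → A | yes | no |
| L → N | A → N | yes | no |
| H → N | A → N | yes | no |
| L → H | A → A | no | no |
| H → L | A → A | no | no |

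The three unchanged pairs are N → N, which stays N → N, and L → L and H → H, which both become A → A.

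1. Nine cells (3 × 3) collapse into four (2 × 2).
2. Six of the nine are changes of category. Four of these six still appear as a shift, and 6 − 4 = 2 do not.
3. None of the six keeps its direction. If k subjects in one arm go from normal to low and k in the other go from normal to high, with all else equal, both arms show k in the same cell.
4. The A → A cell mixes four situations: stable low, stable high, low to high, and high to low. It also holds any deepening within low or within high.
5. With L/N/H categories, all six changes become distinct off-diagonal cells. Worsening within one side (high to much higher, low to lower) still sits on the diagonal, so it needs a grade or a multiple of the limit of normal.

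**How many subjects?** The documents give no share abnormal at baseline for any parameter. As an assumption only, let that share be p, with 77 subjects per arm (SAP section 4). The number starting in the normal row is 77 × (1 − p):

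- p = 20%: 77 × 0.8 = 61.6
- p = 50%: 77 × 0.5 = 38.5
- p = 80%: 77 × 0.2 = 15.4
- p = 90%: 77 × 0.1 = 7.7

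This counts who could show a normal-to-abnormal shift. It does not count who is misrepresented by pooling high and low, nor what a three-category table would recover. That depends on how often subjects leave the range on each side or cross it, and the documents give nothing on either.

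**The case against.** The strongest reply is that nothing is lost from the report and that the SAP does what the protocol specifies.

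- **Change from baseline.** Opposite individual changes cancel in the mean, but they widen the standard deviation and show in the minimum and maximum, by visit and by arm. This stands as a partial safeguard. These statistics are not scaled to local ranges, though. All these tests are run in local laboratories, and the synopsis expects about 120 sites. The shift table is the only planned by-arm laboratory summary tied to those ranges.
- **Adverse events.** Protocol 8.3 says that clinically significant findings that "are present at prior to Day 0 and significantly worsen during the study should be reported as adverse events", and SAP 6.6.1 tabulates treatment-emergent events by maximum severity. That is a genuine between-arm comparison that covers subjects already abnormal at entry. It depends on the investigator judging the finding significant and independent of the underlying condition, which is a demanding filter in this population.
- **Listings and the DMC.** Listings flag out-of-range values but do not compare arms. The DMC may see unblinded reports and subject-level data (Protocol 9.4), but that is monitoring during conduct, not a planned final summary.
- **A later table.** All values are kept, so a three-category table could be made afterwards. That is true, and it is also why specifying it now costs so little.

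Two stronger readings are tempting. A reader might infer that most subjects are abnormal at baseline, so the table is nearly blind. Enrollment does require a patient "To be treated in an ICU at the time of enrollment", with APACHE II 10 to 35, and high and low white cell counts are two of the five alternative entry signs in Protocol 4.1. That makes abnormal baseline values plausible. It does not give a rate, and the rate will differ by parameter. A reader might also infer that separating high from low would expose worsening toxicity in general. It would not, as step 5 of the working shows.

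**Conclusion.** The point holds as a minor limitation of safety presentation. The loss of direction follows from the SAP's own definition and needs no assumption about the population. It affects every parameter of interest on both sides of its range, and much less those where concern runs one way, such as CRP or albumin.

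In terms of categories, two of six changes are hidden and the other four are undirected. In terms of subjects, the size is unknown. There is no contradiction between protocol and SAP, no data are lost, and no efficacy result or hypothesis test depends on it. The remaining outputs soften the gap but do not replace a by-arm table of direction against the local range.

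**What to change.** In SAP 6.6.2, replace normal/abnormal with low/normal/high against the local ranges, which the current definition already needs. Present the 3 × 3 shifts by treatment group:

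- from baseline to each scheduled visit, as now;
- from baseline to the lowest and, separately, to the highest post-baseline value (placed against the local range), because one subject can go out of range on both sides. State whether unscheduled results count.

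To show worsening within one direction, add a by-arm shift in toxicity grade or multiples of the limit of normal, and name the parameters to which it applies.

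The cost is programming. No new data are needed, and the change can be made before the SAP is finalized, which SAP section 1 places before database lock. The short description of shifts in Protocol 9.3.2 can stand, since the SAP table would contain that summary.

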### **Immunogenicity (ADA)**

Immunogenicity (ADA) samples will be obtained at screening/baseline and Day 28. Assays will be performed by a central laboratory.

### **6.6.3. Vital Signs**

Vital signs include heart rate, arterial blood pressure, respiratory rate, and temperature.

Maximum daily temperature (defined as the maximum temperature reported on a single calendar day) will be recorded. Body temperature may be taken per the site's preferred method but limited to oral, tympanic, rectal or core measurements and will be recorded in the appropriate electronic case report form (eCRF). The same method of measuring a patient's body temperature should be used throughout the study.

Descriptive statistics will be used to summarize vital signs measurements and change from baseline by each scheduled key time point.

All vital sign assessments will be listed by subject.

#### **6.6.4. Electrocardiograms (ECG)**

A standard 12-lead ECG will be obtained at baseline for reference. Abnormal ECG finding that would be observed during the course of the study will be duly documented and if appropriate, reported as adverse events.

All 12-lead ECG data will be listed by subject.

#### **6.6.5. Physical Examinations**

A standard physical exam by body systems (General Appearance, Head and Neck, Lymph Nodes, Cardiac, Pulmonary, Abdominal, Genitourinary, Osteoarticular, Extremities, Cutaneous, Neurological) will be performed at baseline, then at Day 4, 7, 14, 21, and 28 or in case of early termination. Changes from baseline will be assessed and if appropriate, reported as adverse events.

Physical exam findings by body systems will be tabulated using counts and percentages at baseline and each scheduled post-baseline visit.

#### **6.7. Interim Analyses**

No interim analysis is planned.

### **7. PROGRAMMING SPECIFICATIONS**

Analyses will be performed using SAS® version 9.3 or higher. All available data will be presented in subject data listings which will be sorted by subject as applicable. Detailed Programming Specifications will be provided in a separate document.
